## TIME AND EVENTS SCHEDULE - OPEN-LABEL EXTENSION PHASE

Study Phase	End of Double -Blind Phase							Open-	Label Tı	eatment	Phase						
Study Week a	Week 12	Week 12+1 Day	Week 12+2 Days	Wee k 13	Wee k 14	Wee k 15	Wee k 16	Wee k 20	Wee k 24	Wee k 28	Wee k 32	Wee k 36	Wee k 40	Wee k 44	Wee k 48	Wee k 52 m	EOS/ Week 54
Visit Number	11	12	13	14	15	16	17	18	19	20	21	22	23	24	25	26	27
Procedures																	
Hospitalization b	C	ontinuou	S	Χb	Χb												
Safety Assessments																	
Weight and waist circumference c	х						X	X	X	X	X	X	X	X	X	X	X
Vital Signs d	X	X	X	X	X	X	X	X	X	X	X	X	X	X	X	X	X
Physical examination e	x						X	X	X	Х	Х	X	Х	Х	X	X	Х
12-lead ECG (triplicate) f	X	X	X	X	X	X	X	X	X	X	X	X	X	X	X	X	X
Safety laboratoriesg	X						X	X		X		X		X		X	X
HbA1c laboratory test	x								X			X				X	X
Urinalysis	X						X	X		X		X				X	X
Pregnancy test (urine)	X						X	X	X	X	X	X	X	X	X	X	X
RDQh			X														
AIMS	X						X	X	X	X	X	X	X	X	X	X	X
S-AS and BARS	X			X	X	X	X	X	X	X	X	X	X	X	X	X	X
Sheehan-STS	X	X	X	X	X	X	X	X	X	X	X	X	X	X	X	X	X
Adverse events								Co	ntinuou	S							
Concomitant medication		Continuous															
Other Laboratory Assessments																	

Study Phase	End of Double -Blind Phase							Open-	Label Tı	eatment	Phase						
Study Week a	Week 12	Week 12+1 Day	Week 12+2 Days	Wee k 13	Wee k 14	Wee k 15	Wee k 16	Wee k 20	Wee k 24	Wee k 28	Wee k 32	Wee k 36	Wee k 40	Wee k 44	Wee k 48	Wee k 52m	EOS/ Week 54
Visit Number	11	12	13	14	15	16	17	18	19	20	21	22	23	24	25	26	27
Pharmacokinetic and concomitant medications sampling 	х	х	х	x	х	х	х	x	х	х	х	х	х	х	х	х	х
Efficacy Assessments																	
PANSS	X				X		X		X		X		X		X	X	X
PSP	X						X		X		X		X		X	X	
CGI-S	X				X		X	X	X	X	X	X	X	X	X	X	X
Verbal fluency test	X						X		X			X				X	
C. 1 35 11 41																	
Study Medication																	
Administration j	X	X	X	X	X	X	X	X	X	X	X	X	X	X	X	X	
Dispense k			X	X	X	X	X	X	X	X	X	X	X	X	X		
Study drug accountability 	X			X	X	X	X	X	X	X	X	X	X	X	X	X	

NOTE: Patients to be contacted via phone at Weeks 18, 22, 26, 30, 34, 38, 42, 46, and 50 to verify safety and to make sure the patient is doing well and is compliant with study medication

Abbreviations: AIMS = Abnormal Involuntary Movement Scale; BARS= Barnes Akathisia Scale; CGI-S = Clinical Global Impression-Severity Scale; ECG = electrocardiogram; EOS = end-of-study; HbA1C = hemoglobin A1c; PANSS = Positive and Negative Syndrome Scale; PSP = Personal and Social Performance; RDQ = Readiness Discharge Questionnaire; S-AS = Simpson-Angus Scale; STS = Suicidality Tracking Scale

#### Footnotes:

<sup>a Visits 14 - 27 may occur  $\pm 2$  days from scheduled visit

b Patients will be hospitalized starting on the morning of the last day of the double-blind treatment phase (Visit 11) up to Visit 13 Hospitalization on Visits 14 and 15 are at the discretion of the investigator to ensure per-protocol ECG assessment and PK sampling are done. Hospitalization includes admission to a hospital or the utilization of an inpatient facility

<sup>c Patients will be weighed clothed (lightly) and without shoes

Minerva Neurosciences, Inc. MIN-101C07 Statistical Analysis Plan

Final Version 1.0

- d Vital signs (blood pressure, heart rate, respiratory rate, and oral or aural body temperature) obtained after the patient is resting in supine position for ≥ 5 minutes. Vital signs during hospitalization are assessed pre-dose within 30 minutes of dosing, and at about 4 hours post dosing. All other assessments are at about 4 hours post dosing.

  a Abbreviated physical examinations at Visits 18, 19, 21, 22, 24 and 25
- f Scheduled ECG recording on Visits 12 through 15 should be done prior to the planned PK sample at pre-dose within 30 minutes of dosing, and at the approximate time of maximum plasma concentration of both MIN-101 (6 to 8 hours post dosing) and BFB-520 (9 to 12 hours post dosing) Scheduled ECG recordings on Visits 16 through 26 should be done prior to the planned PK sample 2-4 hours post dosing after all other assessments have been completed
-  Safety laboratory tests include haematology, serum chemistry (including serum lipid profile, and fasting blood glucose) and prolactin Patients must fast for 8 hours before the blood sample is taken
- h On Week 12 + 2 days or prior to discharge authorization if later than Week 12 + 2 days
- Pre-dose samples (may be done along with the safety laboratory samples, when scheduled) during Visits 12 through 15 and at the approximate time of maximum plasma concentration of both MIN-101 (6 to 8 hours post dosing) and BFB-520 (9 to 12 hours post dosing) PK samples during Visits 16 through 26 should be done pre-dose and 2-4 hours post dosing One sample will be collected at Visit 27 along with the safety laboratory samples A concomitant medication blood sample should be collected coincidental with the PK sample scheduled at the approximate time of maximum plasma concentration of MIN-101 (6 to 8 hours post dosing) during Visit 12 through 15, and 2-4 hours after dosing during Visits 16 through 26 PK samples should follow the ECG (in triplicate) assessments
- j At Week 12 (Visit 11), drug dispensed at Week 8 (Visit 10) must be administered
- k At Visits 12 25 when new blisters are dispensed, the patient should start taking drug from the new blisters
-  Patient's drug intake diary should be collected and reviewed, and new diary dispensed with the new medication blisters
- Every attempt must be made to complete both the Week 52 (Visit 26) and EOS/Week 54 (Visit 27) in case of early termination during the open-label extension phase

## 1.3. GLOSSARY OF ABBREVIATIONS

Abbreviation	Term
AE	adverse event
AESI	adverse event of special interest
AIMS	Abnormal Involuntary Movement Scale
ALT	alanine aminotransferase
ANCOVA	analysis of covariance
AST	aspartate aminotransferase
BARS	Barnes Akathisia Rating Scale
BMI	body mass index
CGI-S	Clinical Global Impression - Severity Scale
$C_{\text{max}}$	maximum drug concentration (in plasma or serum)
CYP	cytochrome
DSB	diastolic blood pressure
DSM-5	Diagnostic and Statistical Manual of Mental Disorders- Fifth Edition
ECG	electrocardiogram
eCRF	electronic case report form
EMA	European Medicines Agency
EOS	end-of-study
F	female
FDA	Food and Drug Administration
HbA1C	hemoglobin A1c
HBsAg	hepatitis B surface antigen
HCV	hepatitis C virus
HIV	human immunodeficiency virus
HR	heart rate
ITT	intent-to-treat
IWRS	Interactive Web Response System
LNL	lower normal limit of laboratory reference range
LOCF	last observation carried forward
M	male
MedDRA	Medical Dictionary for Regulatory Activities

Abbreviation	Term
MINI	Mini International Neuropsychiatric Interview
MMRM	Mixed Model Repeated Measures
NSFS	Negative Symptoms Factor Score
PANSS	Positive and Negative Syndrome Scale
PCS	potentially clinically significant
PD	pharmacodynamic(s)
PK	pharmacokinetic(s)
PO	oral, by mouth (orally)
PP	per-protocol
PSP	Personal and Social Performance
QTc	QT interval value corrected for heart rate
QTcF	QT interval value corrected for heart rate using Fridericia's formula
RDQ	Readiness for Discharge Questionnaire
SAE	serious adverse event
SAF	Safety population
SAP	Statistical Analysis Plan
S-AS	Simpson-Angus Scale
SAS	Statistical Analysis System, former initials of analytics software produced by SAS Institute Inc.
SBP	systolic blood pressure
SD	standard deviation
SE	standard error
SI	Système International d'Unités, the International System of Units
SOC	System Organ Classification (part of MedDRA coding)
STS	Sheehan-Suicidality Tracking Scale
TD	tardive dyskinesia
TEAE	treatment-emergent adverse event
ULN	upper limit of normal
US	United States (of America)
WHO	World Health Organization

## 2. OBJECTIVES

## **Primary Objective**

To evaluate the efficacy of 2 fixed doses (32 mg and 64 mg) of MIN-101 compared to placebo in improving the negative symptoms of schizophrenia as measured by the change from Baseline in the PANSS Marder negative symptoms factor score (NSFS) over 12 weeks of double-blind treatment.

## **Key Secondary Objective**

To assess the effect of MIN-101 compared to placebo on the Personal and Social Performance (PSP) over 12 weeks of double-blind treatment.

#### Secondary and Exploratory Objectives

To assess the effect of MIN-101 compared to placebo over 12 weeks of double-blind treatment on:

- Clinical Global Impression of Severity (CGI-S).
- · Safety and tolerability.

## 3. GENERAL STATISTICAL CONSIDERATIONS

#### 3.1. SAMPLE SIZE AND POWER

The sample size for this study is based on the assumption of a treatment difference of 3 points in the mean change from Baseline to Week 12 in PANSS negative subscale score based on the Marder NSFS between any MIN-101 dose group and placebo. A standard deviation of 6.5 in the change in PANSS negative subscale score from Baseline is used. Assuming an equal allocation to placebo and each of the 2 MIN-101 doses, 100 patients in each treatment arm are required to detect the treatment difference of 3 points with a power of 90% at an overall 2-sided significance level of

0.05. When adjusted for a rate of about 40% of patients who will not have either Baseline or at least 1 on-treatment efficacy assessments, the required number of patients becomes 167 in each treatment arm. Therefore, the total number of patients enrolled across the 3 treatment arms will be 501.

#### 3.2. RANDOMIZATION AND BLINDING

Randomization to the initial double-blind phase (MIN-101 64 mg, MIN-101 32 mg, or placebo in a 1:1:1 ratio) and randomization of patients initially assigned to the placebo arm in a 1:1 ratio to the two active arms, MIN-101 64 mg and MIN-101 32 mg, in the open-label extension phase will be performed as part of a single randomization step at Baseline. Randomization of patients initially assigned to placebo to treatment in the open-label extension phase will be nested within the initial randomization, by assigning the eventual open-label treatment at the outset.

Central randomization will be implemented in this study. Patients will be randomized at Baseline to 1 of 4 treatment arms, based on a computer-generated randomization schedule prepared by or under the supervision of the sponsor before the study. The randomization will be balanced by using randomly permuted blocks and will be stratified by region (United States, all other countries). The Interactive Web Response System (IWRS) will assign a unique treatment code, which will dictate the treatment assignment and matching study drug kit for the patient.

Approximation 501 eligible patients will be randomized in a 2:2:1:1 ratio to the following treatment arms:

- MIN-101 64 mg for the entire study, or
- MIN-101 32 mg for the entire study, or
- Placebo for 12 weeks followed by MIN-101 64 mg dose during the open-label extension phase, or
- Placebo for 12 weeks followed by MIN-101 32 mg dose during the open-label extension phase

The investigator will not be provided with randomization codes. The codes will be maintained within the IWRS, which has the functionality to allow the investigator to break the blind for an individual patient, if needed.

At the outset of open-label extension phase, patients and investigators will be aware they are receiving active MIN-101 but will not have knowledge of the dose being given or the treatment received during the double-blind phase of the study. The study is "open-label" only to the extent of informing that all patients are receiving MIN-101.

Under normal circumstances, the blind should not be broken until all patients have completed the double-blind phase of study and the database is finalized. Otherwise, the blind should be broken only if specific emergency treatment/course of action would be dictated by knowing the treatment the patient is receiving. In such cases, the investigator may in an emergency determine the identity of the treatment by IWRS. Telephone contact with the sponsor or its designee will be available 24 hours per day, 7 days per week.

In the event the blind is broken, the sponsor must be informed as soon as possible. The date, time, and reason for the unblinding must be documented by the investigator, in the appropriate section of the eCRF, and in the source document. The documentation received from the IWRS indicating

the code break must be retained with the patient's source documents in a secure manner (e.g., sealed envelope) so as not to unblind the treatment assignment to the study site, sponsor/contract research organization personnel. The investigator is also advised not to reveal the study treatment assignment to the study site or sponsor personnel.

#### 3.3. HANDLING OF DATA

#### 3.3.1. Strata and Covariates

The primary efficacy analysis and corresponding sensitivity analyses will have Baseline NSFS as a covariate and region (United States [US], all other countries) as a fixed effect. Similarly, secondary endpoints and select additional efficacy analyses will contain covariates of their respective Baseline values and region as a fixed effect.

#### 3.3.2. Examination of Patient Subsets

At present no analyses are planned to examine study results within patient subsets.

#### 3.3.3. Multiple Testing and Comparisons

The study-wise type I error probability for testing the 2 MIN-101 doses versus placebo across both the primary and the key secondary endpoint comparisons will be controlled at the 2-sided 0.05 level using a truncated Hochberg procedure with a truncation parameter of  $\gamma = 1$ .

The primary family of hypotheses and key secondary family hypotheses will be tested using a sequential "gatekeeping" approach with suitable adjustment for multiplicity within the family of primary hypotheses and the family of key secondary hypotheses. A MIN-101 dose versus placebo null hypothesis contrast within the secondary family can only be evaluated when both of the null hypothesis contrasts in the primary family have been rejected.

#### 3.3.3.1. Primary Family of Hypotheses

The adjustment for multiplicity within the family of primary hypotheses (corresponding to the primary endpoint, change from Baseline in NSFS over 12 weeks of treatment) will be evaluated first. The truncated Hochberg procedure with a truncation parameter of  $\gamma = 1$  will be used to assess the results. The procedure will allow the null hypothesis of no treatment difference for both the 64 mg and 32 mg doses versus placebo to be rejected if the largest p-value comparing either of these 2 doses versus placebo is  $\leq 0.05$ . Otherwise, the lowest of these 2 p-values must be  $\leq 0.025$  to allow for rejecting the null hypothesis for the representative dose.

#### 3.3.3.2. Key Secondary Family of Hypotheses

Only when a significant treatment effect is demonstrated in both of the primary comparisons of MIN-101 versus placebo, the key secondary family of hypotheses (corresponding to the key secondary endpoint, change from Baseline in PSP total score over 12 weeks of treatment) will be evaluated and interpreted.

Under the Hochberg procedure, if both primary tests are successful, alpha of 0.05 will be carried over for use in the key secondary comparisons. This alpha would be applied to the two key

secondary comparisons in the same manner as within the primary family of hypotheses, where the null hypothesis of no treatment difference for both the 64 mg and 32 mg doses versus placebo will be rejected if the largest p-value comparing either of these 2 doses versus placebo is  $\leq 0.05$ . Otherwise, the lowest of these 2 p-values must be  $\leq 0.025$  to allow for rejecting the null hypothesis for the representative dose.

## 3.3.4. Missing Data and Outliers

Every effort will be made to obtain required data at each scheduled evaluation from all patients who have been treated. Partial dates will be displayed as captured (without imputation) in subject data listings.

No imputation of data elements will be performed for the primary or key secondary analyses to be submitted to the US Food and Drug Administration (FDA). Pattern-mixture modelling imputation of missing primary and key secondary endpoint data will be performed as part of the primary and key secondary analyses to submit within the European Medicines Agency (EMA) dossier. This approach is detailed in Section 5.2.2.

Sensitivity analyses will be performed to examine the impact of assumptions made for the primary and key secondary analyses as outlined in Section 3.3.4.2.

#### 3.3.4.1. Multiple Imputation Using Pattern-Mixture Modelling

For the analyses to be submitted within the EMA dossier, multiple imputation using a pattern-mixture modelling approach will be used to impute values for missing primary (12-week NSFS) and key secondary (12-week PSP total score) endpoints data. For the US FDA analysis and dossier, however, the pattern-mixture modelling will serve as a sensitivity analysis.

In pattern-mixture modelling, missing values of each 12-week endpoint measure will be imputed using pattern imputation by treatment group. This method factors in that patients with missing outcome data can have different outcome distributions than those without missing outcome data. This method can accommodate when values of the 12-week endpoint measure are not missing at random (non-ignorable or informative missing data) such that missing values might be systematically different from observed values. Predictors will include changes in the 12-week measure from Baseline using existing data measured at prior post-Baseline visits, and additional factors of region, age grouping using median, gender, race, body mass index (BMI) grouping (≤30 kg/m², >30 kg/m²), and treatment group. A total of 30 imputed datasets will be generated, analysis will be performed on multiple imputed datasets, and the results will be combined.

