## 10.1. Sample Size Determination

The sample size for this study is based on the assumption of a treatment difference of 3 points in the mean change from Baseline to Week 12 in PANSS negative subscale score based on the Marder negative factor score between any MIN-101 dose group and placebo. A standard

deviation of 6.5 in the change in PANSS negative subscale score from Baseline is used. Assuming an equal allocation to placebo and each of the 2 MIN-101 doses, 100 patients in each treatment arm are required to detect the treatment difference of 3 points with a power of 90% at an overall 2-sided significance level of 0.05. When adjusted for a rate of about 40% of patients who will not have either Baseline or at least 1 on-treatment efficacy assessments, the required number of patients becomes 167 in each treatment arm. Therefore, the total number of patients enrolled across the 3 treatment arms will be 501.

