#### 5.2.2. Primary Efficacy Analysis

As noted in Section 3.3.4, no imputation of data elements will be performed for the primary analysis to be submitted to the US FDA. Pattern-mixture modelling imputation of missing primary endpoint data will be performed before conducting the primary analysis to submit within the EMA dossier. In both approaches, the estimand and analytic approach of using MMRM to evaluate the potential treatment effects is the same, but the data used to analyze the estimand is different between the US FDA and EMA dossiers.

The PANSS Marder NSFS scores and change from Baseline will be summarized by treatment group and study visit. In addition, the trend in change from Baseline in Marder NSFS scores over the series of visit assessments will be presented graphically.

Change from Baseline to Week 12 in the PANSS Marder NSFS score will be analyzed using a MMRM with fixed effects for treatment group (MIN-101 64 mg, MIN-101 32 mg, and placebo), region, visit, and treatment-by-visit interaction, a random effect for patient within treatment group, and Baseline NSFS as covariate. An unstructured covariance matrix will be used to model the covariance of within-patient scores. The Kenward-Roger approximation will be used to estimate denominator degrees of freedom. Comparison against placebo will be performed with the MIN-101 64 mg and 32 mg doses.

The hypotheses can be expressed as follows:

```
Null Hypothesis (H_0): \muMIN-101 64 mg - \muControl = 0 and \muMIN-101 32 mg - \muControl = 0
```

Alternative Hypothesis (Ha):  $\mu$ MIN-101 64 mg -  $\mu$ Control  $\neq$  0 or  $\mu$ MIN-101 32 mg -  $\mu$ Control  $\neq$  0

where  $\mu$ MIN-101 64 mg and  $\mu$ MIN-101 32 mg refer to the mean change from Baseline to week 12 in the PANSS Marder NSFS score at each of the 2 experimental doses, and  $\mu$ Control refers to the mean change from Baseline to week 12 in the PANSS Marder NSFS score in the placebo arm.

As described in Section 3.3.3.1, the adjustment for multiplicity within the family of primary hypotheses will utilize the truncated Hochberg procedure for the purpose of reporting results. This procedure will allow the null hypothesis of no treatment difference for both the 64 mg and 32 mg doses versus placebo to be rejected if largest p-value of comparing either of these 2 doses versus placebo is at or below 0.05. Otherwise, the lowest of these 2 p-values must be at or below 0.025 reject the null hypothesis for the representative dose.

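### The imputation model for the EMA primary and key secondary analyses does not list the Baseline score, an analysis covariate, and leaves unclear whether the Week 12 score or the change is imputed

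*SAP*

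**What the plan says.** SAP 3.3.4.1 plans multiple imputation by treatment group, with 30 imputed datasets, to "impute values for missing primary (12-week NSFS) and key secondary (12-week PSP total score) endpoints data". For the outcome history it states: "Predictors will include changes in the 12-week measure from Baseline using existing data measured at prior post-Baseline visits". The other listed predictors are region, age split at the median, gender, race, BMI split at 30 kg/m² and treatment group. Neither Baseline NSFS nor Baseline PSP total appears. SAP 3.3.4 refers to section 5.2.2 for detail, but 5.2.2 adds no predictor, and neither do sections 5.2.5 and 7.

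The analysis models do use the Baseline score. SAP 5.2.2 specifies "a random effect for patient within treatment group, and Baseline NSFS as covariate". Section 5.2.5 does the same with Baseline PSP total, and 3.3.1 states the general rule.

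The imputation precedes the EMA primary and key secondary analyses. For the FDA it is a sensitivity analysis only.

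On scale, 3.3.4.1 names the 12-week NSFS and PSP total, which are scores. Sections 3.3.3.1, 3.3.3.2, 5.2.1 and 5.2.4 define both endpoints as changes from Baseline.

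**The concern.** An imputation model should contain at least the covariates of the model that will analyse the completed data. Here Baseline enters only inside the earlier change scores, and its level cannot be recovered from those.

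Two things are at stake. First, if dropout depends on Baseline severity differently in the two arms, imputed values that do not condition on Baseline can shift the treatment contrast. That can happen even when data are missing at random given Baseline. The FDA observed-case MMRM conditions on Baseline and is protected in that situation; the EMA version, which SAP 5.2.2 presents as the same estimand and the same MMRM approach, is not. Second, if the raw Week 12 score is imputed from changes alone, the patient's own starting level is replaced by an arm-average level, which adds noise.

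Many values could be imputed. In the Phase 2b study, 165 of 244 randomized patients completed the double-blind phase (Protocol Table 2), so 79/244 = 32% did not.

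**Working it through.** **1. The plan's own figure.** Inputs from SAP 3.1 and Protocol 10.1: "The sample size for this study is based on the assumption of a treatment difference of 3 points"; "A standard deviation of 6.5 in the change in PANSS negative subscale score from Baseline is used"; "with a power of 90% at an overall 2-sided significance level of 0.05"; "Assuming an equal allocation to placebo and each of the 2 MIN-101 doses"; "When adjusted for a rate of about 40% of patients".

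n per arm = 2(1.960 + 1.282)² × 6.5² / 3² = 98.7, so 99 (stated 100; power at 100 is 90.4%). 100/0.6 = 166.7, so 167, and 3 × 167 = 501. The plan's figure reproduces, and this point does not affect it.

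**2. Why the scale matters only when Baseline is missing.** Let B be Baseline, C the Week 12 change, Y = B + C the Week 12 score and X the other predictors. If C = a + bB + c′X + e, then Y = a + (1 + b)B + c′X + e. The residual is the same, so under linear regression imputation both scales give the same imputed values. Without B the equivalence fails. An imputed Y does not follow the patient's own B, so the implied change Y − B tends to fall one for one with B.

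**3. Simulation inputs.** 167 per arm, one dose against placebo, 40% missing at Week 12, imputation by arm with 30 datasets, Rubin's rules, 800 trials per scenario (Monte Carlo error on power about 1 point). A Week 12 ANCOVA with Baseline stands in for the MMRM contrast. Assumed, because the documents give no figures:
- Baseline SD 4.5
- Baseline-change correlation −0.2 or −0.4
- serial correlation 0.75 per visit step
- SD of change 3.5, 4.5, 5.8 and 6.5 at Weeks 2, 4, 8 and 12
- dropout log-odds of 1 per Baseline SD where dropout depends on Baseline

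Using 40% as the Week 12 missing fraction is also an assumption, because SAP 3.1 attaches that rate to patients lacking a Baseline or any on-treatment assessment.

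*Hand check.* The true slope of change on Baseline is −0.2 × 6.5/4.5 = −0.289. If all dropouts lack post-Baseline data and the raw score is imputed without B, the slope in the completed data should be 0.6 × (−0.289) + 0.4 × (−1) = −0.573. The run gave −0.574.

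**4. Dropout unrelated to Baseline, earlier visits observed.** Bias is about 0 for every model. Power for a true effect of 3:

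| Imputation model | SE, corr. −0.2 | Simulated power | Φ(3/SE − 1.96) | SE, corr. −0.4 | Simulated power | Φ(3/SE − 1.96) |
|---|---|---|---|---|---|---|
| With Baseline | 0.842 | 94.6% | 94.5% | 0.787 | 97.3% | 96.8% |
| Change, no Baseline | 0.844 | 94.3% | 94.5% | 0.802 | 97.0% | 96.3% |
| Raw score, no Baseline | 0.965 | 88.4% | 87.5% | 0.864 | 93.1% | 93.5% |

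The SEs are average SEs from the matching null runs. Raw-score losses are 94.6 − 88.4 = 6.2 and 97.3 − 93.1 = 4.2 points. Including scenarios with the same Baseline-related dropout in both arms, the raw-score loss is 3 to 6 points. The change-scale effect runs from a 0.4-point loss to a 2.5-point gain, and bias stays within 0.08 points.

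**5. Stress case: Baseline-related dropout in opposite directions by arm, earlier visits observed.** Drug benefit is negative and the true effect is −3.

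| Imputation model | Bias (points) | Rejection rate at a true null |
|---|---|---|
| With Baseline | at most 0.04 in size | 4.5% to 4.6% |
| Change, no Baseline | −0.25 to −0.5 | 5.5% to 8.5% |
| Raw score, no Baseline | +2.0 to +2.6 | 62% to 79% |

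The signs would swap if the direction of dropout were reversed between arms.

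**6. Extreme variant.** If every patient missing Week 12 has no post-Baseline rating, the power effect ranges from a loss of about 5 points to a gain of about 4 when dropout does not differ by arm. In the stress case at a true null, bias is −0.83 to −1.72 (change) and +2.18 to +1.28 (raw score). This overstates the trial: Protocol 10.5 limits change analyses to patients with post-Baseline data. It is nearer to PSP than to NSFS, because the first scheduled post-Baseline PSP rating is at Week 4.

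**The case against.** The case on the other side is strong on size.

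- The verb in 3.3.4.1 does not close the predictor list, so the accurate statement is that Baseline is not listed, not that it is barred. This stands.
- The change scale is the more natural reading: both endpoints are defined as changes and the outcome predictors are themselves changes. On that reading the Week 12 score is the patient's own Baseline plus an imputed change. This stands, but the section also names the 12-week scores, so the text does not settle it.
- Exposure is limited. The FDA primary and key secondary analyses impute nothing, and SAP 3.3.4.2 gives the EMA an observed-data sensitivity analysis. The MMRM after imputation still adjusts for Baseline, although that does not repair values already imputed without it.
- Nothing in the documents shows that dropout depends on Baseline differently by arm. Protocol 1.4.2.2 reports relapse of 25% on placebo and 13% on MIN-101 in the Phase 2a study. That makes arm-dependent dropout plausible but does not link it to Baseline score.

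A reader might infer that the EMA analysis necessarily loses power, or that its false-positive rate would be 62% to 79%. The documents support neither. The first needs the raw-score reading; the second needs that reading together with opposite-direction dropout under invented inputs.

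A reader might also want age and BMI entered as continuous predictors. Neither is in the primary analysis model and no effect of the splits was examined, so that is a preference outside this point.

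**Conclusion.** The point holds in a limited form. As written, SAP 3.3.4.1 gives an imputation model that is inconsistent with the analysis model for both endpoints, and it does not make clear which scale is imputed.

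Material bias appeared only when Baseline-related dropout differed between arms. With earlier visits observed, the stress case puts it at about 0.25 to 0.5 points (change) or 2.0 to 2.6 points (raw score) on a true effect of 3. A power cost of about 3 to 6 points arises only if the raw score is imputed from changes alone; on the change scale it is negligible.

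These sizes rest on the assumed inputs listed above and on an ANCOVA in place of the MMRM; region and demographic predictors were not simulated. They show what could happen and do not forecast this trial. The omission itself rests on the SAP text alone.

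**What to change.** In SAP 3.3.4.1, add Baseline NSFS to every imputation step for NSFS and Baseline PSP total to every imputation step for PSP. State whether the Week 12 score or the change is imputed; with Baseline included the two are equivalent under linear regression imputation. Say whether the predictor list is complete.

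The cost is about two lines of SAP text and one extra variable in the imputation code. No new data are needed and the planned 501 patients do not change. Because this defines the EMA primary analysis, it should be settled before the double-blind phase is unblinded.
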